1. OVERVIEW OF KEY CHANGES

The following bulleted list identifies the key changes to the protocol and provides the rationale for each change:

- Updated description of RPC1063 to include metabolite CC112273.
- A 75-day (± 10 days) Safety Follow-up Visit was added to ensure adequate collection of adverse events that could be associated with investigational drug. [REDACTED]
[REDACTED]
[REDACTED]
- [REDACTED]
[REDACTED]
[REDACTED]
- [REDACTED]
[REDACTED]
[REDACTED]
- [REDACTED]
[REDACTED].
- Added details regarding previous RPC1063 trial participation requirement to inclusion criterion #1.
- Added dosing instructions and timing of visits for patients entering the study from the open-label period of Study RPC01-202.
- Added breast cancer resistance protein (BCRP) inhibitors to the list of medications that are prohibited during the trial until the [REDACTED] Safety Follow-up Visit. In a Phase 1 drug-drug interaction study, a strong inhibitor of BCRP, cyclosporine, had no effect on ozanimod exposure, while it approximately doubled the exposure of its active metabolites, RP101988 and RP101075. While the major active metabolite CC112273 is not a substrate of drug transporters, it is unknown if the increase in RP101075 (via RP101988) may also lead to a similar increase in CC112273, which is formed directly from RP101075.
- Added monoamine oxidase inhibitors to the list of excluded medications and the list of medications that are prohibited during the trial and safety follow-up period because in vitro data show that the major active metabolite CC112273 is formed by and inhibits MAO-B. The potential for clinical interaction with MAO inhibitors has not been studied.
- Added CYP2C8 inducers or inhibitors to the list of excluded medications and the list of medications that are prohibited during the trial and safety follow-up period because in vitro data show that the major active metabolite CC112273 is further metabolized by CYP2C8 (and by carbonyl reductase). The potential for clinical interactions with

CYP2C8 inhibitors or inducers has not been studied and therefore co-administration is not recommended.

- Changed “titration” to “dose escalation” throughout the protocol for consistency with other ongoing RPC1063 protocols.
- Added nomenclature and dose equivalency between RPC1063/ozanimod HCl (█ mg, █ mg, and 1 mg) and ozanimod (█ mg, █ mg, and █ mg) for consistency across RPC1063 protocols.
- Removed hemoglobin A1c from the chemistry panel because it is not needed for routine evaluation of patient safety.
- Updated protocol to add new protocol template language regarding handling of product quality complaints for any drug product manufactured by or on behalf of Celgene.
- Updated Sponsor’s address.
- Made minor editorial changes and changes for clarification.

This document summarizes the changes that were made between Protocol RPC01-3102 Version 3.0 (dated 7 June 2016) and Version 4.0 (dated 7 June 2017).

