 - It could not be reasonably explained by the known characteristics of the patient's clinical state, environmental or toxic factors or other modes of therapy administered to the patient
 - It disappears or decreased on cessation or reduction in dose. There are exceptions when an AE does not disappear upon discontinuation of the drug (eg, bone marrow depression, fixed drug eruptions, tardive dyskinesia, etc)
 - It follows a known pattern of response to the suspected drug
 - It reappears or worsens if the drug is re-administered

All efforts should be made to classify the AE according to the above categories.

After initiation of investigational drug, all AEs, regardless of relationship to investigational drug, will be recorded until the patient completes his or her last trial visit.

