14.5 Safety Analyses

Adverse events will be monitored during the trial and the data analyzed with respect to incidence within each parent trial treatment group as well as severity and potential relationship of the AEs to investigational drug.

All AEs with a start date before the first dose date in RPC01-3102, which are ongoing from a previous trial to RPC01-3102, will be listed in the AE data listing and labeled as “Prior Adverse Event.”

Adverse events with an onset date on or after the first open-label dose date in RPC01-3102, or with onset prior to the first open-label dose date in RPC01-3102 that increase in severity on or after the first dose of investigational drug will be considered treatment emergent. Treatment-emergent AEs will be summarized for the Safety population by System Organ Class and Preferred Term and presented in descending order of frequency within each System Organ Class. Serious AEs and AEs leading to discontinuation will be summarized similarly.

Associated laboratory parameters such as hepatic profile, renal function, and hematology values will be grouped and presented together. For each laboratory test, individual patient values outside the standard reference range will be flagged and listed. Shift tables will be produced showing the frequency of shifts from Baseline to the highest and to the lowest on-trial value in and out of the normal range as well as by visit. Changes from Baseline to each visit for each numeric laboratory parameter will also be summarized.

The change from Baseline to each visit for each of the vital sign variables will be summarized. Abnormal vital sign values will be flagged and listed.

The change from Baseline to each visit for each of the ECG parameters will be summarized. An outlier analysis of ECG results will be conducted.

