1. OVERVIEW OF KEY CHANGES

The following bulleted list identifies the key changes to the protocol and provides the rationale for each change:

- The 75-day (± 10 days) Safety Follow-up Visit was extended to a 90-day (± 10 days) Safety Follow-up Visit. [REDACTED]
- Extended the requirements for contraception in females after treatment discontinuation from the 75-day Safety Follow-up Visit to the 90-day Safety Follow-up Visit.
- Extended the requirements for reporting of adverse events (AEs) after treatment discontinuation from the 75-day Safety Follow-up Visit to the 90-day Safety Follow-up Visit.
- The requirement for male contraception was removed. Using safety factor assumptions of tenfold higher concentration in the semen than plasma, a twofold higher dose of ozanimod, and semen levels at the maximum concentration (C_{max}), exposure ratio estimates were negligible for female partners of male patients and do not represent a meaningful risk.
- Added the following Safety Follow-up Visits for up to approximately 80 adult patients: Last dose +1, 4 (± 1 day), 7 (± 2 days), 14 (± 3 days), 21 (± 3 days), and 90 (± 10 days) days. Relevant assessments at these visits include AEs, vital signs, concomitant medications, and the following newly added assessments: Physician's Withdrawal Checklist (PWC-20), Hospital Anxiety and Depression Scale (HADS), and Epworth Sleepiness Scale (ESS). These assessments will also be performed at the [REDACTED] and in all adult patients at the first scheduled visit on study treatment after approval of Protocol Amendment Version 7, in order to provide a baseline assessment while on study drug.
- As described in the “Assessment of Abuse Potential of Drugs” FDA guidance document, an evaluation of abuse potential is most relevant for New Molecular Entities with Central Nervous System activity that have not previously been assessed by the Food and Drug Administration (FDA) for abuse potential. Considering this general guidance, the dependence and withdrawal questionnaires are being included in this protocol to complement the abuse liability data being collected and generated in the Ozanimod Multiple Sclerosis program.
- Updated the section for safety assessments to include newly added dependence and withdrawal assessments.

- Updated safety endpoints section(s) to include newly added assessments for withdrawal/dependence.
- Updated statistics section(s) to include planned summaries for newly added assessments.

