This document summarizes the changes that were made between Protocol RPC01-3102 Version 5.0 (dated 07 Jun 2017) and Version 5.0 (dated 29 May 2018).

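### Post-treatment adverse events were followed for unequal lengths of time across protocol versions and exit routes, while Section 14.5 counts TEAEs with no end date and reports crude incidence only

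*Combined protocol and SAP*

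**What the plan says.** **Length of follow-up.** A Safety Follow-up visit already existed at Version 2.0 (08 May 2015). The log for Version 5.0 then records: "A 75-day (± 10 days) Safety Follow-up Visit was added to ensure adequate collection of adverse events that could be associated with investigational drug". (That entry's title calls both versions 5.0; the next entry dates Version 4.0 to 7 June 2017, so I read the change as 4.0 to 5.0.) The log for Version 7.0 records: "The 75-day (± 10 days) Safety Follow-up Visit was extended to a 90-day (± 10 days) Safety Follow-up Visit". It adds, for AE reporting itself: "Extended the requirements for reporting of adverse events (AEs) after treatment discontinuation from the 75-day Safety Follow-up Visit to the 90-day Safety Follow-up Visit".

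**End of AE recording.** Under Section 13.2.4, AEs "will be recorded until the patient completes his or her last trial visit". Section 13.2.5 separately requires SAEs within 90 days of the last dose to be reported.

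**Exemption.** The Synopsis, Schedule of Events footnote j and Section 8.3.4 release patients from the 90-day visit if they start commercial ozanimod within 14 days of stopping study drug.

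**Analysis.** Section 14.5 treats as treatment-emergent "Adverse events with an onset date on or after the first open-label dose date in RPC01-3102", together with earlier events that worsen after that date. It summarises these for the Safety population, with "the data analyzed with respect to incidence within each parent trial treatment group". It gives no last day for counting, no exposure-adjusted rate and no split by protocol version.

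**The concern.** The amendment log is used here as evidence of how the pooled data were collected. No conflict between the log and the current text is alleged.

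If AE recording stops at the last trial visit and that visit moved twice, two patients who stopped drug at the same point could have been observed for different periods, depending on the version in force. Commercial switchers are a further group whose AE recording may end at their last treatment-period visit. A definition with a start and no end counts whatever was collected, and a crude percentage gives no sign that the collection time differed.

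Long-term safety is the first-listed objective, and the AE tables are the main safety output. At stake is whether a stated incidence can be read as applying to one defined period.

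**Working it through.** The plan states no AE rate, sample-size basis or window calculation, so there is no figure to reproduce.

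**Inputs from the documents**
- First enrolment, estimated: August 2015 (Synopsis).
- Version 5.0: 29 May 2018, visit at 75 ± 10 days, so Day 65 to 85.
- Version 7.0: 22 May 2019, visit at 90 ± 10 days, so Day 80 to 100.
- Earlier visit: day redacted. It precedes Day 75, because the Version 6.0 log gives Section 10.5.3 a title spanning the earlier visit to the 75-day visit.
- Planned maximum treatment: 238 weeks × 7 = 1,666 days.

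By version dates, about 34 months ran under the earliest rule and about 12 months under the 75-day rule. These are calendar intervals, not patient counts or site implementation dates.

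**Assumptions**
- Constant event rate r per patient-year: 0.05, 0.2 or 1.0.
- First window: 30 days, range 14 to 60.
- Time on drug T: 70, 364 or 1,666 days.

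**Step 1. Post-treatment period alone.** P = 1 − exp(−r·w/365.25).

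| r | w = 30 | w = 75 | w = 90 |
|---|---|---|---|
| 0.05 | 0.41% | 1.02% | 1.22% |
| 0.2 | 1.63% | 4.02% | 4.81% |
| 1.0 | 7.89% | 18.56% | 21.84% |

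**Step 2. Total crude incidence.** P = 1 − exp(−r·(T + w)/365.25). For example, with r = 1, T = 70 and w = 30: 1 − exp(−100/365.25) = 23.95%. The last column is the 30-to-90-day gap in percentage points, with the gap for a first window of 60 and of 14 days in brackets.

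| r | T (weeks) | w = 0 | w = 30 | w = 75 | w = 90 | Gap, 30 to 90 |
|---|---|---|---|---|---|---|
| 0.05 | 10 | 0.95 | 1.36 | 1.97 | 2.17 | 0.81 (0.41; 1.03) |
| 0.05 | 52 | 4.86 | 5.25 | 5.83 | 6.03 | 0.78 (0.39; 0.99) |
| 0.05 | 238 | 20.39 | 20.72 | 21.21 | 21.37 | 0.65 (0.33; 0.82) |
| 0.2 | 10 | 3.76 | 5.33 | 7.63 | 8.39 | 3.06 (1.52; 3.89) |
| 0.2 | 52 | 18.07 | 19.41 | 21.37 | 22.01 | 2.60 (1.29; 3.31) |
| 0.2 | 238 | 59.84 | 60.49 | 61.45 | 61.77 | 1.28 (0.63; 1.63) |
| 1.0 | 10 | 17.44 | 23.95 | 32.77 | 35.47 | 11.52 (5.52; 14.92) |
| 1.0 | 52 | 63.09 | 66.00 | 69.94 | 71.15 | 5.15 (2.47; 6.68) |
| 1.0 | 238 | 98.96 | 99.04 | 99.15 | 99.18 | 0.14 (0.07; 0.19) |

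The w = 0 column is the extreme case for a switcher with no post-treatment observation. For rare events the absolute gap hardly changes with time on drug, but its share of the total does: 0.81 of 2.17 at Week 10 against 0.65 of 21.37 at Week 238.

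**Step 3. Share of observation after treatment, w/(T + w).** For 30, 75 and 90 days this is 30.0%, 51.7% and 56.2% at Week 10; 7.6%, 17.1% and 19.8% at Week 52; and 1.8%, 4.3% and 5.1% at Week 238.

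**Step 4. Who can be affected.** A patient dosed in August 2015 reaches 1,666 days (4.56 years) in early 2020, after Version 7.0. On that reckoning, version differences do not reach patients treated for the full 1,666 days, and only the switcher exemption can shorten their follow-up. RPC01-202 entrants start at a redacted visit, so this may not hold for them.

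**Step 5. Pooled effect.** It is the sum, over version and exit route, of the share of patients times the gap for that group. The documents give neither the shares nor the rates, so it cannot be computed.

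**The case against.** **Parent trial.** A reader might infer that AE incidence is confounded by parent trial. Two facts make this tempting. The RPC01-202 entry instructions arrived in the same amendment as the 75-day visit ("Added dosing instructions and timing of visits for patients entering the study from the open-label period of Study RPC01-202"). That trial's open-label period was completed only in November 2019, after Version 7.0. The documents do not support the inference: no follow-up length differs by parent trial, and no exit dates by parent trial are given. Section 14.5 groups by treatment group in the parent trial and plans no between-group test. Dependence on parent trial remains a possibility only.

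**Magnitude.** A reader might take 11.5 points as the error in the tables. It is the gap for one profile: a Week-10 leaver, a high assumed rate and an assumed first window. At the same rate it is about 5 points at Week 52 and about 0.1 at Week 238.

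**Time on drug matters more.** At 1 AE per patient-year, on-treatment incidence alone runs from 17.4% at Week 10 to 99.0% at Week 238. This stands. A common window alone would not make crude incidence comparable, which is why exposure-adjusted rates belong in the fix.

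**A cut-off could hide events.** The longer follow-up was introduced to capture drug-associated events, so removing late onsets from the main tables would demote them. This stands against a simple truncation. A cut-off at the shortest follow-up required of any patient also fails, because for exempt switchers no post-treatment visit is required.

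**Absence is not fully shown.** The log for Version 3.0 refers to a Statistical Analysis Plan, and no separate one is in the supplied text; it could contain an end date. Only the 75-to-90-day step is expressly described as extending AE reporting. SAEs within 90 days are reportable even without a visit, which limits the SAE shortfall under the current version; earlier SAE windows are not visible. These points limit the finding to Section 14.5 as written.

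**Conclusion.** The point holds in a limited form. The log shows three successive lengths of post-treatment follow-up, the current text adds an exempt exit route, AE recording is tied to the last visit, and Section 14.5 neither closes the counting period nor adjusts for time observed. Post-treatment events are therefore unevenly observed across protocol versions and exit routes.

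Under the constant-rate assumption, with a first window of 14 to 60 days, the shortfall against 90-day follow-up for a Week-10 leaver runs from about 0.4 points (0.05 per year, 60 days) to about 15 points (1 per year, 14 days). For a full 238 weeks it is at most 1.6 points over the same range, and at most about 1.9 points (61.77 − 59.84) for a switcher with no post-treatment observation. The size in the pooled tables is unknown. The trial is descriptive, so no test is invalidated; what suffers is the meaning of the reported percentages, chiefly for early leavers.

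**What to change.** In Section 14.5:

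1. Keep the tables of all TEAEs, SAEs and AESIs, and state an end date of last dose plus 90 days. List any onset on Days 91 to 100, which the ± 10-day visit window allows, so that nothing is lost.
2. Add exposure-adjusted incidence rates using each patient's actual days observed, on treatment plus post-treatment.
3. Add an incidence table limited to onset from the first RPC01-3102 dose through last dose plus the shortest Safety Follow-up day set by any protocol version. Flag commercial switchers and count them only for the days actually observed.
4. Tabulate later onsets up to Day 90 separately. The denominator is patients whose protocol version required the 75-day or 90-day visit, excluding switchers exempt from it. Show actual days observed, since patients under the 75-day rule were not followed to Day 90.

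Cost: analysis wording and a few extra tables. No new data are needed and no events are dropped. Unobserved time in early leavers cannot be recovered by any of these steps; they only make it visible.

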1. OVERVIEW OF KEY CHANGES

The following bulleted list identifies the key changes to the protocol and provides the rationale for each change:

- Contraception methods and the frequency of pregnancy testing were aligned with the “Recommendations related to contraception and pregnancy testing in clinical trials” (15 Sep 2014) by the Clinical Trial Facilitation Group. Additionally, the requirement for male contraception was maintained from Inclusion Criterion #2 from the previous version of the protocol.
- The prohibition on concomitant use of CYP3A4 inhibitors and inducers was removed based on the results of the clinical pharmacology study RPC01-1902.
- The prohibition on concomitant [REDACTED] was removed based on the results of the clinical pharmacology study RPC01-1908.
- Timing windows were extended for select visits. These changes were made to provide operational flexibility to the study sites.
- A number of changes were made to clarify previously existing instructions and improve readability.

This document summarizes the changes that were made between Protocol RPC01-3102 Version 2.0 (dated 08 May 2015) and Version 3.0 (dated 7 June 2016).

Receptos, Inc. was acquired by Celgene Corporation, and, effective 29 Jan 2016, Celgene International II Sàrl (“CIS II”), a subsidiary of Celgene Corporation, has assumed responsibility as the sponsor of record for all RPC1063 clinical studies for which Receptos, Inc. was previously named sponsor. Receptos Services LLC (“Receptos”), a wholly owned subsidiary of Celgene Corporation, is and will serve as an authorized representative for CIS II, supporting RPC1063 clinical studies.

Overview of Changes:

- Corrections were made to remove reference to a “maintenance trial” and in some instances replaced with “extension trial”
- The Introduction was updated to include the relevant trial, RPC01-1901 (to support removal of the fasting restriction prior to dosing with RPC1063), to include a third metabolite of RPC1063 due to the addition of RPC01-1901 results, to update the status of completed trials, and to reference the Investigator’s Brochure as the most up-to date source of information about studies within the RPC1063 clinical development program.
- The definition of mucosal healing and histologic remission was updated.
- For the purposes of clarity, complete Mayo score, partial Mayo score, and 9-point Mayo score were listed in the description of other efficacy endpoints.
- Physical examinations and [REDACTED] were removed from the list of safety endpoints as they will not be summarized as change from Baseline.
- The section “Pharmacodynamic Endpoints” was added to include the description of [REDACTED] and [REDACTED]. Text regarding markers of inflammation have been revised throughout the protocol to include examples.
- The required window to complete vital signs was removed.
- Instruction to take RPC1063 in a fasted state was removed based on results of the food effect study (Study RPC01-1901).
- The requirement that patients should enter the trial [REDACTED]
[REDACTED].
- Instruction for patients not to take study medication from the prior trial until Visit [REDACTED] during which they will receive RPC01-3102 study medication was added.
- The timepoint after which patients will begin to have additional visit assessments at [REDACTED]
[REDACTED].
- A full examination of the skin for lesions was added as a procedure required for the interim physical examination.
- The window to complete endoscopies was changed from [REDACTED] to within [REDACTED] of the visit date to allow adequate time for completion of procedures. The Day [REDACTED] endoscopy does not need to be repeated if an endoscopy has been completed within [REDACTED].

- [REDACTED]
- [REDACTED]
- Table 2 - footnote d describing pulse monitoring guidelines was updated.
- Inclusion criterion #4 removed “Are capable of providing” to emphasize that the subject must provide informed consent.
- Added a time window for which treatment with a live vaccine should be exclusionary for exclusion criteria #1.
- For clarification purposes and to maintain consistency with protocol RPC01-3101, additional detail (P450 3A4) was added to the CYP3A4 description.
- “Calcium channel blockers” was replaced with examples of calcium channel blockers in exclusion criteria #2. QT interval prolonging drugs with a known risk of torsades de pointes were removed from the exclusion.
- [REDACTED]
- [REDACTED]
- [REDACTED]
- [REDACTED]
- [REDACTED].
- For clarification purposes, the statement patients will be encouraged to complete the trial was revised to only note that the patient may voluntarily withdraw from the trial at any time.
- The definition of “withdrawal by patient” was clarified to note that patients who discontinue study medication will be withdrawn from the study.
- Additional clarity was added to describe dosing (added [REDACTED] to be taken).
- Correction was made to ensure that prior medication history is captured starting at the date of informed consent. The phrase “date of informed consent” was removed from the description of concomitant medications.
- QT prolonging drugs were removed from the list of excluded medications [REDACTED]
- [REDACTED]
- Methotrexate was added as an example of an immunosuppressive agents.
- Tofacitinib was added as an excluded medication.
- Proprietary names for components (eg, chemical excipients or capsules) and packaging of investigational and commercial drug products have been removed in favor of using generic terms. This has been done to simplify the text and limit the use of trademarked or registered names.
- Instructions to the Investigator regarding investigational drug accountability along with record transfer and on site destruction were deleted.
- For clarification purposes, [REDACTED] was changed [REDACTED] for documentation of history of prior medications.
- Details regarding colonic biopsies have been revised.

- For the purpose of clarity, the time period in which stool frequency and rectal bleeding diary entries will be used to calculate Mayo Score was further defined. Additional details regarding calculation of Mayo Score was deleted since this will be outlined in the Statistical Analysis Plan.
- The details of the condition in which ECGs will be performed were revised.
- [REDACTED]
- Criteria #2 for additional extended monitoring of first dose heart rate was revised.
- An additional directive for the requirement of Medical Monitor approval if retest is required to be repeated > 2 times was added. Additional text was added to clarify that repeat laboratory safety testing would be analyzed by the local laboratory.
- Criteria for repeating hematology laboratory results were added.
- A correction was made to section titled “Handling Missing Data” to delete instructions if no post-baseline values are available since all patients in this study will have post-baseline values available from the parent study (RPC01-3101).
- Details on the version of Declaration of Helsinki were removed since the version varies based on region.

Global Changes:

- The Sponsor name and address were changed.
- Confidentiality language was modified.
- The Medical Monitor’s company was updated.
- A Celgene International II Sàrl signatory was added.
- The list of abbreviations was updated, as appropriate.
- References to “Receptos, Inc.” and “Receptos” were modified.
- Minor typographical corrections

[REDACTED]

This document summarizes the changes that were made between Protocol RPC01-3102 Version 1.0 (dated 20 April 2015) and Version 2.0 (dated 08 May 2015).

Overview of Changes:

- Vitals signs assessment was added to Safety Follow-up visit
- Erroneous text relating to questionnaires was removed.
- Minor corrections
